#### **3.2 General study level definitions**

##### **3.2.1 Relative day**

The relative day of a given date “D” will be calculated as follows:

- For days prior to the first BRV administration:  
D – date of first BRV administration
- For days on or after date of first BRV administration and prior to or on the day of last BRV administration:  
D – date of first BRV administration + 1
- For days after the last BRV administration:  
D – date of last BRV administration  
A “+” will be shown at the start to denote posttreatment days

Hence, the first day of BRV administration is Day 1, the day before the first BRV administration is Day -1, and the day after the last dose of BRV is Day +1. Relative day will not be calculated for partial dates.

### 3.2.2 Visit 4, Month 12/Withdrawal Visit

Patients with early study termination (ie, those who complete the Study Termination [Dropout] CRF page), will have their Visit 4 (Month 12/Withdrawal) visits prior to the preferred visit window for Month 12 of greater than or equal to 330 days after date of first BRV administration. Patients completing the study (ie, those who complete the Study Termination NIS [Completed Subject] CRF form), will have their Visit 4 (Month 12/Withdrawal) visits within the preferred visit window for Month 12 of greater than or equal to 330 days after date of first BRV administration. Therefore, Visit 4 will be analyzed as follows depending on the objective and variable being analyzed:

- Visit 4 (Month 12): Including only patients who are study completers with a Visit 4 within the preferred visit window for Month 12 of greater than or equal to 330 days after the date of first BRV administration.
- Visit 4 (Month 12/Withdrawal): Including all data recorded at Visit 4 (ie, completers or patients who withdraw early)

In addition, Visit 4 (Month 12/Withdrawal) visits that correspond to scheduled visits will be included in the counts for the scheduled visits to which they correspond. To be classed as corresponding to the scheduled visit, the withdrawal visit must fall into the windows provided below and the patient have no scheduled visit already available. Only the variables below will have the mapping of withdrawal visits applied.

Variables	Visit 2, Month 3	Visit 3, Month 6
Disposition (Patients attending each visit)	30-135	136-329
Seizure Frequency	30-135	136-329
QOLIE	30-135	136-329
CGIC/PGIC	30-135	136-329
EpiTrack	No mapping as no scheduled visit	150-210

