#### **4.6 Use of subsets of subjects**

All effectiveness analysis will be performed on the FAS and the modified FAS to estimate the effectiveness for patients using BRV per the approved SmPC.

In addition, the responder analysis and the seizure freedom analysis will be repeated on the FAS and modified FAS for:

- patients who completed the study
- patients who discontinued the study due to a lack of efficacy

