### 8.2.2.3 Analysis of seizure frequency related variables

The following tables will be produced on the FAS and all tables except the by subgroup tables will be repeated on the modified FAS:

- Descriptive statistics of the POS frequency at Visit 1 (Baseline), Visit 2 (Month 3), Visit 3 (Month 6), Visit 4 (Month 12), and Visit 4 (Month 12/Withdrawal)
- Descriptive statistics of the absolute reduction in POS frequency (seizures per 28 days) from Visit 1 (Baseline) to Visit 2 (Month 3), Visit 3 (Month 6), Visit 4 (Month 12), and Visit 4 (Month 12/Withdrawal)

- Descriptive statistics of the absolute reduction in POS frequency (seizures per 28 days) by subgroups described in [Section 4.8](#), from Visit 1 (Baseline) to Visit 2 (Month 3), Visit 3 (Month 6), Visit 4 (Month 12), and Visit 4 (Month 12/Withdrawal).
- Descriptive statistics of the percent reduction in POS frequency (seizures per 28 days) from Visit 1 (Baseline) to Visit 2 (Month 3), Visit 3 (Month 6), Visit 4 (Month 12), and Visit 4 (Month 12/Withdrawal)
- Number and percentage of responders ( $\geq 50\%$  reduction) at Visit 2 (Month 3), Visit 3 (Month 6), Visit 4 (Month 12), and Visit 4 (Month 12/Withdrawal)
- A sensitivity analysis of the responder analysis will be performed on two subsets of the FAS and modified FAS as defined in [Section 4.6](#) (patients who completed the study and patients who discontinued the study due to lack of efficacy).
- Number and percentage with seizure freedom (using the 2 methods described in [Table 8–1](#)) at Visit 2 (Month 3), Visit 3 (Month 6), and Visit 4 (Month 12)
- A sensitivity analysis of the seizure freedom analysis will be performed on two subsets of the FAS and modified FAS as defined in [Section 4.6](#) (patients who completed the study and patients who discontinued the study due to lack of efficacy).
- Number and percentage with seizure freedom (using discontinuations counted as seizure freedom = no) by subgroups described in [Section 4.8](#), at Visit 2 (Month 3), Visit 3 (Month 6), and Visit 4 (Month 12)

The following by-patient listings of seizure data will be produced on the All Subjects Documented set:

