### 8.3.1.2 Analysis of QOLIE-31-P scores

All QOLIE-31-P analyses will be performed on the FAS and the modified FAS.

Descriptive statistics will be presented for QOLIE-31-P: 7 multi-item subscales, the health status item, and total score, and the changes from Visit 1 (Baseline) to Visit 2 (Month 3), Visit 3 (Month 6), Visit 4 (Month 12) and Visit 4 (Month 12/Withdrawal). As described in [Section 3.2.2](#), Visit 4 (Month 12/Withdrawal) visits will be mapped to the appropriate scheduled visit and Visit 4 (Month 12) will only include patients completing the study.

The number and percentage of patients with clinically meaningful changes in QOLIE-31-P total and subscale scores from Baseline (improvement, no change, or worsening) will be presented for Visit 2 (Month 3), Visit 3 (Month 6), Visit 4 (Month 12) and Visit 4 (Month 12/Withdrawal).

A question glossary and by-patient listings of QOLIE-31-P scores (including all items of the subscale scores, the total subscale scores, the total score, the health status item, changes from Baseline, and whether patients achieved a clinically meaningful change) will be provided for the All Subjects Documented set.

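### Month 12 holds completers only while Months 3 and 6 also hold later dropouts, so by-visit trends in POS reduction, QOLIE-31-P and CGIC/PGIC mix selection with change

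*SAP*

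**What the plan says.** SAP 3.2.2 defines two versions of Visit 4. The Month 12 version is described as "Including only patients who are study completers with a Visit 4 within the preferred visit window", that is, at 330 days or later. The Month 12/Withdrawal version is described as "Including all data recorded at Visit 4 (ie, completers or patients who withdraw early". Protocol 12.2 makes the same split.

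The same SAP section carries early withdrawal visits back to the scheduled visits: withdrawal "visits that correspond to scheduled visits will be included in the counts for the scheduled visits to which they correspond". For seizure frequency, QOLIE and CGIC/PGIC, a withdrawal visit on Day 30-135 can count as Month 3 and one on Day 136-329 as Month 6. The condition is that "the withdrawal visit must fall into the windows provided below and the patient have no scheduled visit already available". SAP 8.3.1.2 restates both rules together for QOLIE-31-P: "visits will be mapped to the appropriate scheduled visit and Visit 4 (Month 12) will only include patients completing the study".

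The results are tabulated side by side. SAP 8.2.2.3 reports responders "at Visit 2 (Month 3), Visit 3 (Month 6), Visit 4 (Month 12), and Visit 4 (Month 12/Withdrawal"), with the same four time points for absolute and percent POS reduction. SAP 8.3.1.2 and 8.3.3 use these time points for QOLIE-31-P and CGIC/PGIC.

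Three further rules matter:

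- SAP 4.2: missing outcomes are not imputed.
- SAP 3.1: continuous variables are summarized on available observations; categorical percentages are, in general, taken over the whole analysis set with a row for missing.
- SAP 4.6: "the responder analysis and the seizure freedom analysis will be repeated on the FAS and modified FAS for" study completers and patients who stopped for lack of efficacy. No other variable has this repeat.

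**The concern.** Read across, the Month 3, 6 and 12 columns look like one series, but they describe different groups. A patient who leaves on Day 200 is in Months 3 and 6 and absent from Month 12. A difference between columns can come from patients changing, from dropouts leaving the summary, or from both, and the planned tables for POS reduction, QOLIE-31-P and CGIC/PGIC do not separate these.

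It is reasonable to expect dropouts to do worse, though not certain. Under Protocol 8.2 a patient whose physician permanently stops BRV is withdrawn, and lack of effectiveness and AEs are named among the reasons. If dropouts do worse, a higher mean reduction at Month 12 than at Month 6 could be read as growing benefit when it only reflects their absence.

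**Working it through.** **Inputs from the SAP.** Mapping windows 30-135 and 136-329; Month 12 is completers at 330 days or later (3.2.2); available-case continuous summaries and analysis-set N for percentages (3.1); FAS of 385 and the example of 50% retention (2.4).

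**The plan's own figure.** 1.96² × 0.50 × 0.50 / 0.05² = 384.2, rounded up to 385. It reproduces and is used below only as N. The plan gives no figure for drift between visits.

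**Assumptions, not in the documents.** Dropout is uniform over Days 1-329; Visit 2 is on Day 90 and Visit 3 on Day 180; every withdrawal visit takes place; each patient's outcome is constant, so any trend comes only from who is counted. Retention is varied.

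**Who is counted.** Dropouts leaving on Day 30 or later are in Month 3: 300/329 = 0.912 of them. Those leaving on Day 136 or later are in Month 6: 194/329 = 0.590. None are in Month 12. At 50% retention:

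- Month 3: 385 × (0.50 + 0.50 × 0.912) = 368
- Month 6: 385 × (0.50 + 0.50 × 0.590) = 306
- Month 12: 385 × 0.50 = 192

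**Continuous summaries.** With r the retention, f the fraction of dropouts counted, and C and D the means in completers and dropouts:

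mean = [r × C + (1 − r) × f × D] / [r + (1 − r) × f]

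For r = 0.50, C = 40, D = 0, Month 3 is 20 / 0.956 = 20.9 and Month 6 is 20 / 0.795 = 25.2.

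| Retention | Mean % reduction, completers / dropouts | Month 3 | Month 6 | Month 12 | Month 12/Withdrawal |
|---|---|---|---|---|---|
| 50% | 40 / 0 | 20.9 | 25.2 | 40.0 | 20.0 |
| 50% | 40 / 40 | 40.0 | 40.0 | 40.0 | 40.0 |
| 50% | 40 / 50 | 44.8 | 43.7 | 40.0 | 45.0 |
| 70% | 40 / 0 | 28.8 | 31.9 | 40.0 | 28.0 |
| 70% | 40 / 50 | 42.8 | 42.0 | 40.0 | 43.0 |

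**Percentages.** Suppose 50% of completers and 20% of dropouts are improved. The sequence then depends on the denominator:

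| Retention | Denominator | Month 3 | Month 6 | Month 12 |
|---|---|---|---|---|
| 50% | Observed at visit | 35.7% | 38.9% | 50.0% |
| 50% | Analysis set (SAP 3.1) | 34.1% | 30.9% | 25.0% |
| 80% | Observed at visit | 44.4% | 46.1% | 50.0% |
| 80% | Analysis set (SAP 3.1) | 43.6% | 42.4% | 40.0% |

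**Share due to mapping.** Without mapping, only dropouts leaving on or after the scheduled visit day are counted: 240/329 at Month 3 and 150/329 at Month 6. The 40 / 0 case at 50% retention becomes 23.1, 27.5, 40.0. The rise falls from 19.1 to 16.9 points, so mapping adds 2.2.

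**Effect of the fix.** Restricted to the Month 12 patients, every row gives the completer value at all three visits (40.0, or 50.0%), with no drift.

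**The case against.** Several objections carry weight.

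- **Much is already visible.** Month 12/Withdrawal stands beside Month 12 for every variable named here, n is displayed, attendance by visit is tabulated, and response already has a completer repeat. In the 40 / 0 case at 50% retention, Month 12/Withdrawal returns to 20.0, which would alert a careful reader. This stands in part: that row pools withdrawal visits from all times, so it shows that the completer figure is selective but is not a same-patient series.
- **The analysis is descriptive.** The primary variable is 12-month retention, and each secondary seizure-frequency variable runs from Baseline to one visit. That limits the weight of the point.
- **Completer rows can flatter the drug.** They lift Months 3 and 6 to the completer level. This is correct, so the rows need their label and a reading beside Month 12/Withdrawal.

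A reader might also infer stronger versions that the documents do not support.

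- **That outcomes rise over time by construction.** The sign depends on how dropouts compare with completers, which is not given. The percentages fall under the SAP 3.1 denominator.
- **That withdrawal-visit mapping is the cause.** It contributes a small part; the completers-only Month 12 set contributes the rest. Mapping brings otherwise missing dropout data into Months 3 and 6.
- **That the Month 6 window is wrong and should end at Day 270.** That is the midpoint of 180 and the 360-day target in SAP 8.1.1, but Table 8-1 takes Day 330 as the Month 12 target, giving (180 + 330)/2 = 255. A late withdrawal visit enters Month 6 only if Visit 3 is missing, and a shorter window would leave it in no scheduled-visit column. The limit is a matter of preference.

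**Conclusion.** The point holds in a limited form. The by-visit columns describe different populations, and for absolute and percent POS reduction, QOLIE-31-P and CGIC/PGIC no same-patient series is planned, so a trend across them cannot be read as change in patients.

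For available-case continuous summaries the drift is upward if dropouts do worse, zero if they do equally well, and downward if they do better. With the assumed means of 40 and 0 it is 19.1 points at 50% retention and 11.2 at 70% (40.0 − 28.8). These sizes rest on assumed outcome contrasts and uniform dropout and are not forecasts. For CGIC/PGIC and QOLIE-31-P meaningful change, the general denominator rule makes percentages tend to fall as dropouts become missing. SAP 8.3.1.2 and 8.3.3 do not restate the denominator, so it needs confirming.

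The primary retention analysis and the sample size are unaffected. This is an inexpensive improvement in interpretability.

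**What to change.** 1. Extend the completer-only repeat in SAP 4.6 and 8.2.2.3 to absolute and percent POS reduction, QOLIE-31-P scores and change (8.3.1.2) and CGIC/PGIC (8.3.3). Show Months 3 and 6 in the patients who form the Visit 4 (Month 12) column, with n at each visit, since some completers may have missed a visit.
2. Use these rows for any statement on change over time, label them as completers, and present them beside the Month 12/Withdrawal result.
3. State the denominator of each categorical by-visit table (analysis set with a missing row, or patients observed).

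The mapping windows can stay as they are. The cost is more tables: existing shells repeated on a subset close to the completers already named in SAP 4.6, plus short notes. No new data are needed.

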### 3.2.3 Date of first administration of BRV

Date of first administration will be defined as the date of first BRV administration on the "First Administration of Drug" CRF page. If there is no data related to BRV medication (i.e. on the "First Administration of Drug" CRF page, "Brivaracetam Medication" CRF page, or study termination pages) available, then it is assumed the patient did not take BRV, and date of first administration will not be imputed. If the date of first BRV administration is missing on the

"First Administration of Drug" CRF page, then the first non-missing date on the "Brivaracetam Medication" CRF page will be used as the first BRV administration date. In case of a partial date, then use the imputation of partial first BRV administration date rules as described in [Section 4.2.2](#). Otherwise the Visit 1 date will be used. This means that for example if a patient has a non-missing date for "Date of last administration of medication (Brivaracetam) while in the study" on the study termination page, no dates on the "First Administration of Drug" CRF page, "Brivaracetam Medication" CRF page then the Visit 1 date will be used.

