## 12.1 Definition of analysis sets

The All Subjects Documented set is defined as all patients included in the study with valid data consent and for whom at least Visit 1 (Baseline) is documented. The All Subjects Documented set will be used for patient disposition and patient data listings only.

The Safety Set (SS) is defined as all patients included in the All Subjects Documented set for whom it cannot be excluded that they received treatment with BRV at least once in the study. The SS will be used for the analysis of the safety data and Baseline characteristics of the patients.

The Full Analysis Set (FAS) is defined as all patients in the SS who did not receive BRV before entering this NIS. The FAS will be used for the analysis of BRV retention (ie, the primary variable) and the secondary and other variables.

The modified FAS is defined as all patients in the FAS who are treated according to the approved SmPC during their Observation Period, representing the on-label use of BRV in Europe.

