## **12.4 Determination of sample size**

Initially, a sample size of 430 patients was chosen for this study in order to obtain 385 patients in the FAS, which allows for approximately 10% of patients to not be included.

When the sample size is 385, a 2-sided 95.0% CI for a single proportion using the large sample normal approximation will extend 0.05 from the observed proportion for an expected proportion of 0.50. As an example, given an observed retention rate of 50%, a sample size of 385 patients would give a 2-sided 95% CI of 45% to 55% based on the large sample normal approximation to the binomial distribution.

However, since the first 100 patients were all enrolled at sites in Germany in early 2016 and the enrollment in that country was closed, it was believed that ongoing enrollment in other countries would be following different best practices in BRV usage, which could lead to wide variation in this NIS. For this reason, 100 additional patients are planned to be enrolled to obtain 385 patients in the FAS at non-German sites.

It is, therefore, planned to have 530 patients in this NIS. Withdrawals will not be replaced.

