### **3.2.4 Date of last administration of BRV**

Date of last administration of BRV will be defined as last administration of BRV while in the study as recorded in the Study Termination (Dropout) or (Completed Subject) CRF pages. If the date is partial, then use the imputation of partial end dates rules as described in [Section 4.2.2](#).

For the snapshot analyses described in [Section 4.3](#), patients ongoing in the study will not yet have a date of last administration of BRV recorded. For these patients the date of last administration of BRV will be imputed using the date of the data cut off so that an estimate of the exposure to date can be calculated.

For patients who have completed or withdrawn from the study, if the date of last administration is missing, then the last end date from the BRV Medication CRF page (applying the imputation of partial end dates rules as required) will be used. If that date is also missing then the date of first BRV administration as described in [Section 3.2.3](#) will be used. If all of the above are missing, then it is assumed the patient did not take BRV.

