### **3.5 Analysis sets**

The All Subjects Documented set is defined as all patients included in the study with valid data consent and for whom at least Visit 1 (Baseline) is documented. The All Subjects Documented set will be used for patient disposition and patient data listings only.

The Safety Set (SS) is defined as all patients included in the All Subjects Documented set for whom it cannot be excluded that they received treatment with BRV at least once in the study. Evidence of BRV dosing will be determined based on patients meeting 1 or more of the following criteria:

- At least 1 entry with a total daily dose >0 recorded in the BRV Medication (NIS) CRF page
- A present date of first BRV administration during observational study, recorded in the First Administration of BRV CRF page
- A present date of last BRV administration while in the study, recorded in the Study Termination (Dropout) or Study Termination (Completed Subject) CRF pages

The SS will be used for the summary of the safety data, Baseline characteristics of the patients, and important protocol deviations.

The Full Analysis Set (FAS) is defined as all patients in the SS who did not receive BRV before entering this NIS. Any patients with a documented protocol violation of Selection Criterion #1 will be considered to have been treated with BRV prior to inclusion in this NIS and will be excluded from the FAS. The FAS will be used for the analysis of BRV retention (ie, the primary variable), the secondary variables, and other variables.

The modified FAS is defined as all patients in the FAS who are treated according to the approved SmPC during their Observation Period, representing the on-label use of BRV. Compliance with the approved SmPC is defined as follows:

- Patient has POS with or without secondary generalization at Baseline (ie, patient does not have a protocol violation of Selection Criterion #5)
- All documented BRV doses were less than or equal to the maximum approved dose of 200mg/day
- BRV doses were greater than or equal to the minimum approved dose of 50mg/day (with the exception of down-titrating). Per the SmPC, a down-titration of BRV is allowed to 20mg/day, hence any patients receiving BRV doses lower than 50mg/day from day 2 onwards will be reviewed during the DEM to determine whether they are taking BRV per SmPC.

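### The SAP requires recorded evidence of BRV dosing where the protocol includes by default, so treated patients with no BRV entries would drop out of the retention denominator, undeclared and unquantified

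*SAP*

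**What the plan says.** Protocol 12.1 defines the SS as the documented patients "for whom it cannot be excluded that they received treatment with BRV at least once in the study". The opening of the SS definition in SAP 3.5 uses the same wording. On that definition, missing information keeps a patient in.

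SAP 3.5 then makes the definition operational: "Evidence of BRV dosing will be determined based on patients meeting 1 or more of the following criteria". There are three criteria:

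- "At least 1 entry with a total daily dose >0 recorded in the BRV Medication (NIS) CRF page"
- a first-dose date on the page that records the start of BRV
- a last-dose date on either study termination page.

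The date rules carry the matching assumption. Where no BRV data exist on any of the relevant pages, SAP 3.2.3 states: "then it is assumed the patient did not take BRV, and date of first administration will not be imputed". SAP 3.2.4 ends its chain of fallbacks for the last dose with: "If all of the above are missing, then it is assumed the patient did not take BRV".

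The FAS is drawn from the SS (SAP 3.5) and is the denominator for 12-month retention (SAP 8.1.1). Retention at 3 and 6 months uses the same method (SAP 8.2.1). The All Subjects Documented set supports disposition and listings only. SAP 3.9, which lists departures from the protocol's analyses, names an EpiTrack addition and the omission of one seizure-freedom summary. It does not mention the SS rule.

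**The concern.** The two rules treat an absence of data in opposite ways. Under the protocol, a patient with blank BRV pages is unknown and stays in. Under the SAP criteria, the same patient is presumed untreated and goes out. The design does not make that presumption the natural one: Visit 1 takes place after the decision to start BRV (Protocol Table 17-1, footnote a), and Protocol 5 describes it as the first day of treatment.

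The evidence list is also narrower than the evidence the study holds. An adverse event with BRV withdrawn sits in the pharmacovigilance database (SAP 10.2), and a Medication Discontinuation page exists (SAP 5.1), but neither counts towards the SS. SAP 3.2.3 accepts any date on the Brivaracetam Medication page as the first dose, whereas SAP 3.5 needs a dose above zero on that page. A dated entry with the dose missing, and nothing else, yields a first-dose date but no place in the SS.

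What is at stake is the primary estimate. A treated patient who left no BRV entry would hardly ever be someone who stayed on BRV for 330 days. Leaving such patients out removes failures only. The modified FAS and Kaplan-Meier analyses in SAP 8.1.2 start from the same FAS, so they inherit the exclusion and cannot reveal it.

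**Working it through.** **1. Who leaves the denominator.** Set membership is decided in SAP 3.5; SAP 3.2.3 and 3.2.4 govern dates and state the matching presumption.

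| Patient documented at Visit 1 | In SS and FAS? | 12-month retention |
|---|---|---|
| Lost early, first-dose date only | Yes | Last dose falls back to the first-dose date (3.2.4): not retained |
| Lost early, dose above zero recorded but no date | Yes | First dose set to Visit 1 (3.2.3), last dose to the same date: not retained |
| No dose above zero, no first-dose date, no last-dose date; BRV taken | No | Not counted; would almost certainly be a failure |
| Same blanks; BRV never taken | No | Rightly not counted |

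For the FAS, the table assumes no earlier BRV use. Only the third row is an error.

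**2. The plan's own figures reproduce.** Protocol 12.4 takes 50% retention, a half-width of 0.05 and a FAS of 385 from 430 enrolled, "which allows for approximately 10% of patients to not be included".

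- n = 1.96² × 0.25 / 0.05² ≈ 384.1, rounded up to 385. The half-width at 385 is 1.96 × √(0.25/385) = 0.0499.
- 385 / 0.9 = 427.8, so 428 against the stated 430. The implied allowance is 45 of 430, or 10.5%.

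**3. Effect on retention.** Let F be the FAS size, R the retention in it, and k the number of treated, non-retained patients left out. Restoring them changes retention from R to R·F/(F + k), a drop of R·k/(F + k). The documents do not give k, so the values below are assumptions. With F = 385 and R = 0.50 (192.5 retained):

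| k | Retention with k restored | Drop (points) |
|---|---|---|
| 0 | 50.0% | 0 |
| 1 | 192.5/386 = 49.9% | 0.13 |
| 5 | 192.5/390 = 49.4% | 0.64 |
| 10 | 192.5/395 = 48.7% | 1.27 |
| 20 | 192.5/405 = 47.5% | 2.47 |
| 45 | 192.5/430 = 44.8% | 5.23 |

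The last row gives the whole enrolment allowance to this one mechanism. That is an implausible ceiling, because the allowance also has to cover earlier BRV use and patients who were truly untreated.

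**4. Sensitivity to F and R.** Scaling the FAS to the current plan of 530 gives 385 × 530/430 ≈ 475. Ten patients left out then cost 0.50 × 10/485 = 1.03 points at 50% retention and 0.70 × 10/485 = 1.44 points at 70%.

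**The case against.** The strongest case against the point is that the exposed group should be very small and may consist largely of patients who are rightly left out. BRV initiation date and daily dose are Visit 1 items (Protocol Table 17-1), early discontinuers should have Visit 4 data collected, and missing data are a target of central monitoring and data-cleaning checks (Protocol 13.1 and 13.2.2). A patient with nothing on any BRV page may well be one who was due to start after Visit 1 and never did. That patient has no treatment on which to be retained. All of this stands as an argument about size. It does not show that the group is empty, and on-site monitoring is for cause only, so recovery of blank pages is not assured.

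A second objection is that the information is already visible. SAP 5.1 lists excluded patients with reasons, and the by-patient retention listing in SAP 8.1.1 covers the All Subjects Documented set. That is right as to the count, which can be recovered. But no planned retention estimate uses it.

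A third objection is that rewriting the SS to follow the protocol literally would do harm. Patients with no sign of exposure would enter the adverse-event denominators and dilute incidence. Each would also receive a one-day exposure under the formula in SAP 10.1 (last minus first plus 1) and a Day 1 time in the Kaplan-Meier analysis of discontinuation due to adverse drug reactions. This stands, and it is why the change below leaves the SS alone.

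A reader might go further and infer that patients lost early generally fall out of the denominator, or that retention is overstated by about 5 points. The documents support neither. One qualifying entry keeps a patient in, and the fallbacks then count an early loss as a failure. The 5-point figure is the ceiling in the table, not an estimate.

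**Conclusion.** The conflict is real: it lies between the protocol and the SAP, and within SAP 3.5 itself, and SAP 3.9 does not declare it. Its effect on retention at 3, 6 and 12 months runs one way, upward, on the assumption that treated patients with no BRV entry were not retained. The size is unknown. It is about 0.1 point per such patient at a FAS of 385 and 50% retention, and zero if none of the patients left out was treated. Ten such patients would shift the estimate by 1.27 points, about a quarter of the planned half-width of 5.0.

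The documents do not establish that retention is in fact overstated, since they give neither the number of documented patients without BRV data nor the share of them who took the drug. In a descriptive single-arm study, and with a group that is probably small, this is a minor point. It is worth correcting because the correction is cheap and the exclusion can otherwise favour the primary result unseen.

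**What to change.** - **SS.** Keep the evidence-based rule for the safety tables, and declare it in SAP 3.9 as a departure from the definition in Protocol 12.1.
- **Count.** Report the number of documented patients with no qualifying BRV entry, and how many of them are confirmed as never having started BRV.
- **Retention.** Add one sensitivity row, with its exact confidence interval, at 3, 6 and 12 months. Its denominator is the FAS plus the documented patients who have no qualifying entry, are not confirmed as never having started BRV, and had no earlier BRV use. Apply the SAP's existing fallbacks (first dose set to the Visit 1 date, last dose set to the first-dose date), so that they count as not retained. As far as this mechanism goes, the main row and this row then bracket the answer.
- **Alignment.** Bring SAP 3.5 into line with 3.2.3, so that a dated Brivaracetam Medication entry with a missing dose counts as evidence of dosing.

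The cost is a few sentences of SAP text, one count and one table row. The downside is a slightly less favourable retention figure in that row, which may include a few patients who never took BRV. The safety denominators change only for patients admitted by the alignment of 3.5 with 3.2.3.
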